### 9.2.1 Treatment Assignment Procedures

The randomization protocol and the randomization process are prepared and executed by investigators from the Biostatistics and Design Team through the secure web-based data management system, so that eligibility is automatically confirmed, and records are current. The study statisticians have developed the randomization protocol to ensure that sufficient baseline and eligibility data are entered and validated before participants are randomized into the study.

Randomization will be performed stratified on sex, and will use blocked randomizations. Recruitment will target equal numbers of men and women and 23% minority participation. All study personnel, except for the Biostatistics Team will be blinded to the randomization table. We do not anticipate the need to break the randomization code with any urgency, but should it be necessary, it will be decided by the four PIs, with input from the NIH Project Officer. The Study Physician and/or Medical Safety Officer will review descriptions of safety events in an un-blinded manner.

## 9.3 Interim analyses and Stopping Rules

No formal stopping rules are planned for this pilot study. Interim analyses on data quality and safety will be provided to the DSMB. Safety data will be provided by randomized group to the DSMB in a closed session.

## 9.4 Outcomes

### 9.4.1 Primary feasibility outcomes

a) Degree of sustained CR (**Benchmark 1**): CR > 10% at 9 months;

- b) TRE sustainability (Benchmark 2):** At least 75% of participants eating within window on >80% of days; and
- c) Retention of study participants (Benchmark 3):** Retention > 85% at 9 months.

#### 9.4.2 Secondary outcomes

##### Secondary

- Body weight change assessed using home scales at baseline, 6 and 9 months
- Changes in fat and lean body mass assessed by DXA at baseline and 9 months
- Change in bone mineral density assessed by DXA at baseline and 9 months
- Change in resting energy expenditure assessed by indirect calorimetry at baseline and 9 months
- Change in physical activity energy expenditure assessed by ActivPAL at baseline and 9 months
- Change in energy intake assessed at baseline and 9 months using doubly-labeled water
- Change in total muscle mass at baseline and 9 months assessed by d3 creatine (d3cr)
- Change in self-reported energy intake assessed using the ASA24 at baseline and 9 months
- Change in physical and cognitive function assessed at baseline and 9 months
- Change in age-related biomarkers at baseline and 9 months

HALLO-P will also collect the following information to guide the design of a longer-term study.

##### HALLO-P Feasibility Benchmarks

- Community Interest – Response rates to mailings and other outreach
- Recruitment Yields – Ratio of initial contacts to randomizations
- Participants with Inter-current Health Events – Health events that suspend intervention participation
- Intervention Delivery Costs – fixed and variable costs associated with each intervention arm

#### 9.5 Data Analyses

##### 9.5.1 Primary Feasibility Analyses.

Our **primary feasibility outcome (Benchmark 1)** will be absolute rather than relative Energy Intake change to avoid the loss of efficiency and power that has been criticized relative to the direct modeling of ratio measures (110, 111). The primary analyses of DLW-based EI will use constrained mixed linear models (cLDA), with both baseline and follow-up values as model outcomes, to estimate within-group pre-post changes in EI, with group assignment as the primary variable of interest, adjusted for sex (113). We note that the constrained, linear mixed model is extremely flexible, constrains pre-randomization group means to be equal, allows for both intent-to-treat analyses by including participants with incomplete data, and permits inclusion of random effects related to group-based interventions; the traditional ANCOVA can be shown to be one specific parameterization of this model. Kenward et al. (114) note that with proper use of REML

estimation, the constrained, mixed model and ANCOVA are equally efficient (115). Lu (2010) notes that for within group estimation, which is a focus of this pilot study analyses, the ability to include participants with partial data can have advantages relative to reducing bias due to missing data (113).

From these models, the primary finding of interest is whether each group's least squares mean EI one-sided 90% (80%) lower confidence interval excludes the mean value for an average 10% reduction in caloric intake at 9-months based on the mean baseline EI. In addition, using results from this model, we will estimate percent change in EI with a bootstrapped 90% (80%) one-sided confidence interval to provide direct estimates of the relative reduction. Because participants are “grouped” for a component of each intervention, intra-class correlations will be estimated to characterize the dependence of response within intervention groups. Sensitivity analyses will be performed to determine how the width of confidence intervals may depend on the ICC and these analyses will be performed within all randomized groups.

For **Benchmark 2**, we will use Clopper-Pearson 90% (80%), one-sided confidence intervals to provide a lower limit on the estimate of the proportion of individuals consuming calories within the 8-hour (+/- 30 min) window on 80% of days (i.e., each participant will receive a yes/no categorization as to whether they consumed calories within the window on > 80% of days) based on self-report. Marginal models for binary outcomes will also be used to explore the magnitude of the ICC for this outcome. This calculation will also be performed using proportion of days as a continuous outcome based on self-report or data from continuous glucose monitors (TRE group). When considered a continuous outcome, methods identical to those outlined for Benchmark 1 can be used.

For **Benchmark 3**, the primary outcome will be the proportion of participants that complete the 9-month follow-up exam. As for Benchmark 2, Clopper-Pearson exact 90%, one-sided confidence intervals will be used to put lower limits on these estimates. Marginal models for binary outcomes will also be used to explore the magnitude of the ICC for this outcome.

Supporting analyses will also be carried out within subgroups defined by sex and race/ethnicity.

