### Study Schematic

### Interventions and Duration

**In-Person Caloric Restriction:** This group will undergo a 9-month behavioral diet intervention targeting a 20% reduction in caloric intake. During the first 6 months, participants will meet in-person one time each month individually and three times/month in a group setting with a dietitian and/or behavioral coach. During the remaining three months of intervention, there will be one group and one individual meeting each month. Participants will keep diet records using the Fitbit app on a tablet and weight using a BodyTrace™ smart scale that transmits data through a study-specific Companion App. Participants will use wrist-worn Fitbit step monitors to track their physical activity and receive feedback via the app, with a goal to promote movement across the day, continuously increasing their daily step count. This arm was discontinued for the last wave (4) of the study to permit more participants to be randomized into the other two arms.

**Remote Caloric Restriction:** This group will have a similar 20% reduction in caloric intake and frequency of meeting schedule, and similar physical activity goal as the in-person arm. However, the remote arm intervention will be delivered via video conferencing.

**Time-restricted Eating:** This group will undergo a 9-month dietary intervention targeting consumption of all daily caloric intake within an 8-hour window of time, with no restrictions on caloric intake. During the first 6 months, participants will meet in-person once per month individually and three times per month in a group setting with a dietitian and/or behavioral coach. During the remaining 3 months of intervention, there will be one group and one individual meeting each month. Participants in TRE will be asked to log into the study-specific Companion App each day to document the beginning and end of their feeding cycles with timing of meals/snacks consumed. As in the CR arms, participants will use wrist-worn Fitbit step monitors to track their physical activity and receive feedback via the app, with a goal to promote movement across the day, increasing daily step count. Continuous glucose monitoring will be used at intervals to document glucose levels over a 10-day period.

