### **Sample Size and Population**

The HALLO-P target population is older adults with an indication for weight loss for whom participation is feasible and safe. Approximately to one-hundred participants will be randomized to the three study arms in a 1:1:1 ratio for the first 66 participants. The remaining participants enrolled will be randomized with equal probability to the remote CR and TRE groups. Randomization is stratified by sex.

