### **3 STUDY DESIGN**

**Overview.** HALLO-P is a 9-month randomized behavioral intervention trial to pilot three strategies to change the amount or timing of food intake in order to evaluate these strategies for use in a long-term trial. The three strategies include 20% CR delivered in-person, 20% CR delivered remotely, and TRE within an 8-hour window each day. All participants will also receive an intervention to reduce sedentary time and increase the number of daily steps.

**Inclusion / Exclusion.** HALLO-P's recruitment target is approximately 100 older (60+ years), community-dwelling men and women residing in Forsyth County, NC or surrounding counties who have obesity ( $BMI = 30 - \leq 40 \text{ kg/m}^2$ ) or are overweight ( $BMI = 27 - <30 \text{ kg/m}^2$ ) with an indication for weight loss (e.g., hypertension, hyperlipidemia, elevated waist girth, controlled diabetes). We will target up to 50% men but expect to be in the range of 35%-45% men, 50%  $> 70$  yrs, and  $> 23\%$  minority participants which reflects racial demographics of our region.

HALLO-P will exclude persons for whom the interventions are potentially unsafe, who have a history of eating or nutritional disorders, who are likely to drop out due to severe chronic illness or other reasons, or who show inability to perform self-monitoring activities required by the interventions. We will exclude those doing shift work because disturbances in circadian cycles may interfere with TRE. We will exclude persons with uncontrolled or previously undetected diabetes because disease management may interfere with the interventions and certain medical treatments may complicate outcome interpretation.

**Randomization / Study Duration.** Recruitment is scheduled to last approximately 12-15 months. Once eligibility is established and baseline testing is completed, participants will be randomized using blocked randomizations stratified by sex to one of the 3 intervention groups for the first 66 participants and blocked randomizations stratified by sex to either the remote CR or TRE groups for the remainder of the cohort. Randomized participants will be in the intervention for 9 months.

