### **5.1.2 The HALLO-P Interventions**

Overall Design. For the first 6 months of intervention, participants in all three groups will meet as follows: (a) 1 time each month individually with a behavioral coach and/or a Registered Dietitian (RD) as needed; and (b) 3 times per month in a group setting. The groups will be formed in waves as participants join the study with the size of each group between 8-12 participants. Participants in the CR group will keep diet records using a smartphone/tablet (study to provide) and record home weight using a BodyTrace™ electronic smart scale that transmits data to the center automatically and provides a vehicle for interventionists to adapt the intervention as needed for each participant. Those in TRE will log into the app each day to document the beginning and end of their feeding cycles with timing of meals/snacks consumed. These data also provide a vehicle for interventionists to adapt the intervention as needed as in the CR group. It is also important to note that all 3 intervention groups include a physical activity component that aims to have participants "move more and move more often across the day." We will provide Fitbit step monitors as a means of tracking activity with the initial goal of increasing daily steps by 20% from baseline levels and spreading out movement across the day and incorporating additional weight-bearing physical activity such as step-ups and stair climbing. To ensure participants' understanding of the requirements of their intervention assignment, each participant will receive a brief group-specific nutrition orientation following randomization but prior to the start of the intervention. Likewise, each participant will receive a brief group-specific technology orientation designed to build confidence in the use of technology following randomization and before the start of the intervention. The group sessions will be used to create a sense of community with others, educate and discuss with participants the health benefits of

either CR or TRE, share experiences with the interventions, and facilitate group problem solving. During months 7-9 of the intervention, there will be one group and one individual meeting each month.

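### The Benchmark 1 model assumes one baseline energy intake for all three arms, but in-person CR closed before wave 4, so randomization supports that for in-person CR only within waves 1-3 (minor)

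*Combined protocol and SAP*

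**What the plan says.** Section 9.5.1 fits baseline and 9-month EI from doubly-labeled water jointly, "with group assignment as the primary variable of interest, adjusted for sex". It states that the model "constrains pre-randomization group means to be equal" and that it "permits inclusion of random effects related to group-based interventions". The finding of interest is whether each group's one-sided 90% bound "excludes the mean value for an average 10% reduction in caloric intake at 9-months based on the mean baseline EI". The section does not say whether that baseline mean is pooled or arm-specific.

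On allocation, the Précis (Interventions and Duration) says of in-person CR: "This arm was discontinued for the last wave (4) of the study". The Précis (Sample Size and Population) gives 1:1:1 for the first 66 participants and then: "The remaining participants enrolled will be randomized with equal probability to the remote CR and TRE groups". Section 3 describes the second stage as "blocked randomizations stratified by sex to either the remote CR or TRE groups for the remainder of the cohort". Section 9.1 expects about 24 participants in wave 4, 22:34:34 randomized in all, and about 20:30:30 with both measures. Section 5.1.2 says of the delivery groups: "The groups will be formed in waves as participants join the study".

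No section adds wave or allocation period to the model, or limits the baseline constraint to participants randomized concurrently.

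**The concern.** A constrained baseline is justified because randomization makes expected baselines equal. That argument covers only people who could have been assigned to the same arms. Remote CR and TRE share a 1:1 allocation in both periods, so equality between them holds throughout. In-person CR shares an allocation with the other two only for the first 66.

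The model therefore compares the in-person follow-up with a pooled baseline that includes people who could not have entered that arm. If wave 4 starts from a different EI, part of the difference is reported as intervention effect. Benchmark 1 is judged arm by arm, so this reaches a primary feasibility conclusion: in-person CR would pass slightly too easily if wave 4 baseline EI is higher, and slightly too rarely if it is lower.

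**Working it through.** **The plan's own figures (Section 9.2).** The smallest passing reduction is 0.10 x baseline + t(0.90, n-1) x 250/sqrt(n).
- n = 30: 259.9 kcal/day (13.0%) at baseline 2000, and 309.9 (12.4%) at 2500.
- n = 20: 274.2 (13.7%) and 324.2 (13.0%).

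All four agree with the plan and are not in dispute. The in-person half-width is 274.2 - 200 = 74 kcal/day.

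**Wave 4 shares (Section 9.1).** In-person 0/22 = 0; remote CR and TRE 12/34 = 35.3% each; pooled 24/90 = 26.7%.

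**Bias formula.** With slope b of follow-up on baseline EI, the constrained estimate of an arm's change is its observed change + (1 - b) x (arm baseline mean - pooled baseline mean). Suppose wave 4 EI is shifted by D at both visits. The in-person baseline then lies (24/90)D below the pooled mean, and its reduction is overstated by (1 - b) x (24/90) x D.

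**Slope.** The SD of change of 250 is from the plan. Baseline SD and D are assumptions. With equal variances at the two visits, the within-period covariance is SD² - 250²/2 = SD² - 31250. A model with no period term estimates its own slope, and the drift inside remote CR and TRE raises it. The average within-arm variance added by drift is (68/90) x (12/34) x (22/34) x D² = 0.1725 D². Hence 1 - b = 31250 / (SD² + 0.1725 D²).

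Example, SD 300 and D = 300: 1 - b = 31250 / (90000 + 15529) = 0.296. The bias is 0.296 x 0.2667 x 300 = 23.7.

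**Threshold.** If the 10% threshold uses the pooled baseline mean, it rises by 0.10 x (24/90) x D = 2.7, 5.3 or 8.0 for D = 100, 200 or 300. This offsets part of the bias as long as b is below 0.9. Net = gross - threshold shift.

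| Baseline SD | Gross, D = 100 / 200 / 300 | Net of pooled threshold |
|---|---|---|
| 300 | 9.1 / 17.2 / 23.7 | 6.4 / 11.9 / 15.7 |
| 400 | 5.2 / 10.0 / 14.2 | 2.5 / 4.7 / 6.2 |
| 500 | 3.3 / 6.5 / 9.4 | 0.6 / 1.2 / 1.4 |

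Units are kcal/day of overstated in-person reduction; negative D reverses the signs. Simulation of the planned fit agrees at the upper end: gross 23.6 at SD 300 and 14.0 at SD 400 for D = 300.

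At SD 400 with a waves 1-3 mean of 2000, a true 10.0% reduction is estimated as (200 + 5.2)/2026.7 = 10.1% to (200 + 14.2)/2080 = 10.3%.

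**Remote CR.** Its baseline lies (12/34 - 24/90)D = 0.086D above the pooled mean. The net effect is an understated reduction of (1 - b - 0.1) x 0.086 x D: at most 0.196 x 0.086 x 300 = 5 kcal/day (SD 300, D = 300).

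**Simulated in-person false-pass rate.** The true reduction is exactly 10%, nominal rate 10%, pooled threshold, slope estimated, 8,000 runs per cell, Monte Carlo SE about 0.3 points.

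| Baseline SD | No shift | +100 / +200 / +300 | -200 |
|---|---|---|---|
| 300 | 9.2% | 11.9 / 14.9 / 16.2% | 5.7% |
| 400 | 9.7% | 10.6 / 11.4 / 11.4% | 8.1% |
| 500 | 9.5% | 9.9 / 9.9 / 10.5% | 9.2% |

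**If enrolment reaches about 100.** Wave 4 would be 34 and its pooled share 34%. At SD 400 and D = 200, the added variance is (78/100) x (17/39) x (22/39) x D² = 0.1918 D², so 1 - b = 31250 / (160000 + 7672) = 0.186. The gross bias is 0.186 x 0.34 x 200 = 12.7 rather than 10.0, and the net is 12.7 - 6.8 = 5.9 rather than 4.7.

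**The case against.** The strongest reply is that the size is undetermined and probably small. Drift, baseline SD and slope all come from outside the documents; with no drift the constraint is harmless. Sex adjustment already removes any drift that comes only from a changing sex mix. Section 9.1 puts feasibility ahead of between-group testing and makes in-person CR the smaller arm because the team knows that intervention best. All of this stands, and it is why the point is minor.

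A second reply is that delivery groups follow waves, and the model can carry random effects for them. This stands in part. The plan permits such effects and will estimate intra-class correlations, but it does not specify the form. A group intercept on both visits, with group SD assumed to be half the shift, holds the gross bias to about 3-8 kcal/day. A group effect at follow-up only removes none of it.

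Three stronger readings are tempting, and the documents do not support them:
- **That drift is established.** The revision log widens BMI to 40 kg/m² in May 2023 and closes the in-person arm in July 2023. That makes a shift plausible, but no section reports BMI or baseline EI by wave.
- **That the threshold compounds the bias.** The constrained model has a single baseline mean (given sex), so the natural reading of the criterion is pooled, and a pooled threshold offsets the bias while the slope is below 0.9. Larger false-pass rates need this model paired with a waves 1-3 threshold, which the plan does not describe.
- **That the problem extends to other analyses.** Section 9.5.2 states no baseline constraint for secondary outcomes, and Benchmarks 2 and 3 use exact intervals for proportions.

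**Conclusion.** The point holds as a minor flaw in the specification of the primary Benchmark 1 model. Its logic rests on the documents alone: a common baseline for three arms, adjustment for sex only, and one arm closed before the last wave.

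Its size rests on assumptions: a wave 4 shift of 100-300 kcal/day that remains after sex adjustment and is equal at both visits, and a baseline SD of 300-500. On those, the in-person reduction is misstated by about 3-24 kcal/day gross and 1-16 net of a pooled threshold, against a half-width of 74. At SD 400 the false-pass rate moves to 10.6-11.4%; only the low-SD, large-shift corner reaches 16.2%. Remote CR barely moves. The documents do not show that any such shift occurred, so nothing here says that the in-person result will be wrong.

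**What to change.** Add randomization period (waves 1-3 versus wave 4) and period-by-time to the Benchmark 1 model, so that the baseline constraint applies within period. Define the baseline mean used for each 10% threshold and evaluate the least squares mean at the same mix: waves 1-3 for in-person CR, and the arm's own observed period mix for remote CR (planned 22:12).

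Keep the interaction. With a period main effect alone, a wave 4 response differing by 100 kcal/day would add 1.3-3.8 kcal/day of in-person bias; period-by-time removes it. If the team prefers the main effect in the primary model, the interaction version should be a stated sensitivity analysis.

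The cost is a short change to Section 9.5.1 and two model terms, with period known for every participant. The in-person standard error goes from 52.0 to 52.4, 53.7 to 54.0 and 54.5 to 54.7 kcal/day at baseline SD 300, 400 and 500; for remote CR it rises by under 0.1. The sample-size figures in Section 9.2 need no change.

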### **5.1.1 The Use of a mHealth Platform for Adaptive CR and TRE Interventions**

Technological innovations (web-connected tablets, wearable monitors, and smart scales) now allow for behavior change strategies to extend into a person's daily life and to be adaptive in near real time to participants' progress. These tools offer improved approaches for self-monitoring key processes central to either CR or TRE and support other action plans important to successful treatment. Specific to the CR intervention, we will use an equation using in-home weights (captured with the smart scale) to model and monitor adherence to CR in real time, a strategy that was successful in CALERIE (82, 86) and will be adapted for HALLO-P. For the TRE intervention, we will track adherence to feeding schedules via the app using a Feedogram visual self-monitoring and feedback tool to quickly identify problems that arise. Importantly, interventionists also see the data from the app in real time and, when participants fall outside a "zone of adherence", they can tailor strategies based on the conceptual model and toolbox discussed in greater depth in a separate document. A study-specific app named the *Companion App* will provide immediate reinforcement for achieving goals via mastery badges (87) and allows for interactive communication between participants and the intervention team. HALLO-P builds on experience garnered in several CR interventions with older adults for the past 4 years; (58, 87, 88) which has led to the development of methods to engage older adults in the design of the mHealth applications and provides hands-on training to optimize older adults' comfort and confidence in use of the technology (58, 88).

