## **9 STATISTICAL CONSIDERATIONS**

### **9.1 General Design Issues**

As suggested by multiple authors (106-108), the design and sample sizes for our HALLO pilot study have been chosen to focus on the feasibility of the design of the targeted full-scale study, rather than on power for hypothesis testing between groups.

During the HALLO pilot, we target the enrollment of approximately 100 participants meeting the inclusion/exclusion criteria to one of three intervention arms 1) 20% CR delivered in-person; 2) 20% CR delivered remotely via video conferencing; and 3) 8-hour TRE with *ad libitum* calorie intake for the first 3 waves (66pts) and the fourth wave will randomize ~24 pp to one of two intervention arms including 20% CR delivered remotely and 8-hour TRE groups. We anticipate randomizing 22:34:34 participants with fewer participants being in the in-person CR group since our group (and others) has more experience with that intervention. From those randomized, we anticipate approximately 20:30:30 participants to complete both pre-and post-measures at 9 months. Data from the enrollment process will be used to refine recruitment criteria, estimate recruitment yields, and test and refine intervention approaches. The pilot will inform three design benchmarks: **a)** The degree of sustained CR (**Benchmark 1**): CR > 10% at 9 months; **b)** TRE sustainability (**Benchmark 2**): At least 75% of participants eating within window on >80% of days; and **c)** **Benchmark 3**: Retention > 85% at 9 months.

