### **9.2 Sample Size and Randomization**

Sample sizes for each group in the pilot study were determined by focusing on the width of 90%, one-sided confidence intervals, as used previously for pilot projects (109). For **Benchmark 1**, the 20% CR interventions will be considered successful if the mean reduction in DLW-assessed weight-maintaining energy intake (EI) provides evidence that the %CR is >10% of the baseline mean (e.g., >200 kcal/day reduction from 2000 kcal/day). This level was chosen because it is approximately the lower end of the range of CR associated with benefits in animal models. Our **primary outcome** will be absolute rather than relative EI change to avoid the loss of efficiency and power from the direct modeling of ratio measures (110, 111). Analyses will be based on constrained, mixed linear models described in Section 9.5. The primary quantity of interest is whether each group's least squares mean EI one-sided 90% lower confidence interval excludes the mean value for an average 10% reduction in caloric intake based on the mean baseline EI.

**Benchmark 1.** Within the remote CR group with ~30 paired observation (i.e., 10% LTFU), and a conservative SD of 250 kcal/day for change in EI, as calculated from CALERIE, we project a 90%, one-sided confidence intervals will have a lower bound excluding 200 kcal/day (a 10% reduction from a baseline mean of 2000 kcal/day) if we observe a 260 kcal/day or greater reduction (a 13% reduction). In a case where the baseline mean intake is 2500 kcal/day, a 310 kcal/day reduction (12.4%) would result in a confidence interval that excludes a 10% reduction in EI (112). With 20 evaluable participants in the in-person CR group, these percentages increase to 13.7% (for a baseline mean of 2000 kcal/day) and 13% (for a baseline mean of 2500 kcal/day). Note that these calculations assume the ICC capturing the dependence of change in EI resulting from group-based interventions is zero. Should the ICC arising from group-based intervention delivery be large enough to inflate the variance of the within-group mean by as much as 10%, a slightly larger observed decrease in EI will be needed to rule out a 10%

reduction. If the target is met for both CR groups, practical and economic considerations will be considered in developing the intervention for the larger trial.

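### Benchmark 1's two-time-point model does not correct for dropout related to poor adherence, and the weights already collected that could help are left out of it

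*Combined protocol and SAP*

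**What the plan says.** Section 9.5.1 analyses DLW-based EI with a constrained longitudinal model (cLDA). Its outcomes are the baseline and follow-up EI values, with group as the variable of interest and adjustment for sex. The section says that the model "allows for both intent-to-treat analyses by including participants with incomplete data" and that, for within-group estimation, "the ability to include participants with partial data can have advantages relative to reducing bias due to missing data". The only sensitivity analysis it names for Benchmark 1 concerns the intra-class correlation. It names no auxiliary variable, no imputation and no missing-data sensitivity analysis.

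Section 9.4.2 gives the measurement times: "Change in energy intake assessed at baseline and 9 months using doubly-labeled water". Section 5.4 adds that EI change is calculated from the DLW change together with the DXA change, so both 9-month measurements are needed.

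Weight is measured more often. For the CR arms, Section 5.1.1 says "we will use an equation using in-home weights (captured with the smart scale) to model and monitor adherence to CR in real time". Section 5.4 makes scale weight a secondary measure of CR adherence, and the schedule in Section 6.1 has a clinic weight at 6 months in every arm. In the analysis plan, weights appear only in the separate secondary and exploratory analyses (Sections 9.5.2 and 9.5.4).

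**The concern.** A mixed model gains most from partial data when someone who drops out has left intermediate outcome values. Here there are none. For a participant without 9-month EI, the model in effect uses the expected change of completers with the same arm, sex and baseline EI. If those who miss the 9-month measurement had restricted less than such completers, the estimated arm mean is too favourable.

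Benchmark 1 asks whether caloric restriction is sustained, and its answer feeds the choice of intervention for the larger trial. Adherence-related dropout is therefore the kind of missingness that bears most directly on the question, and it is the kind that baseline-only records cannot correct.

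**Working it through.** **Inputs**
- Confidence level, Section 9.2: "Sample sizes for each group in the pilot study were determined by focusing on the width of 90%, one-sided confidence intervals".
- SD, Section 9.2: "a conservative SD of 250 kcal/day for change in EI, as calculated from CALERIE".
- Numbers, Section 9.1: "We anticipate randomizing 22:34:34 participants", with 20:30:30 expected to have both measurements. Missing: 4/34 = 11.8% remote and 2/22 = 9.1% in-person.
- Margin, Section 9.2: 200 kcal/day, which is 10% of a 2000 kcal/day baseline.

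**Step 1: reproduce the plan's thresholds.** The required observed reduction is margin + t(0.90, n−1) × 250/√n.
- Remote, n = 30: 200 + 1.311 × 45.64 = 259.9 kcal/day (13.0%). The plan states 260.
- In-person, n = 20: 200 + 1.328 × 55.90 = 274.2 kcal/day (13.7%). The plan states 13.7%.
- At a 2500 kcal/day baseline the same formula gives 309.9 (12.4%) and 324.2 (13.0%), also as stated.

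The stated thresholds therefore reproduce, and they are completer figures.

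**Step 2: what the model does with a baseline-only record.** With two time points, the cLDA estimate equals a regression of 9-month EI on arm and baseline EI among completers, evaluated at the baseline mean of everyone randomized. A direct likelihood fit to simulated three-arm data (no sex term) gave the same arm reductions as this regression: 272.02, 270.55 and 80.00. The unadjusted completer changes in those data were 244.08, 286.55 and 80.23. So baseline-only records do affect the estimate, but only through baseline EI.

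**Step 3: let the missing restrict less.** Suppose that participants missing 9-month EI restrict by a fraction f of the completer mean, and let p be the fraction observed. The all-randomized mean is then the completer mean × [p + (1−p)f]. For its lower limit to reach 200, the completer mean must be

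200 / [p + (1−p)f] + t × 250/√n.

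| Arm | f = 1 | f = 0.5 | f = 0 |
|---|---|---|---|
| Remote, p = 30/34 | 200 + 59.9 = 259.9 | 212.5 + 59.9 = 272.4 | 226.7 + 59.9 = 286.5 |
| In-person, p = 20/22 | 200 + 74.2 = 274.2 | 209.5 + 74.2 = 283.7 | 220.0 + 74.2 = 294.2 |

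If zeros are instead entered for the missing and the SD and t limit are recomputed on all 34 or 22, the f = 0 figures become 291 and 299. Hence the ranges 287 to 291 and 294 to 299.

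**Step 4: the decision at and away from the threshold (remote, f = 0).**
- Completer mean 260: all-randomized mean 260 × 30/34 = 229, lower limit 173 to 176 depending on method. This fails.
- Completer mean 400 (the 20% target): mean 400 × 30/34 = 353, lower limit about 293 with zeros entered. This passes clearly.

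**Step 5: an illustration of the mechanism.** A simulation of the remote arm (4000 runs, N = 34) set the true reduction at exactly 10% and let dropout depend on poor 6-month weight loss. The weight–EI correlation (0.5 to 0.9) and the baseline EI SD (350 kcal/day) are also assumptions; the documents give none of these. With 11.8% missing, the planned model estimated 218 to 232 kcal/day instead of 200 and passed 19% to 29% of the time, against a nominal 10%. Adding 6-month weight change brought these back to about 200 and about 10%. The auxiliary here is the variable that drives dropout, so this is a favourable case for the remedy.

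**The case against.** Much can be said for the plan.
- **The wording is hedged.** Section 9.5.1 says only that partial data can have advantages. Baseline-only records do handle dropout related to baseline EI, and they inform the baseline mean from which the 10% target is derived.
- **Follow-up continues after stopping.** Section 8 keeps those who discontinue the intervention in follow-up, with their permission, and invites them to the 6- and 9-month visits. Only those who miss the 9-month DLW or DXA are affected. Retention is itself a primary benchmark, so the loss will be visible.
- **Poor adherence among the missing is not documented.** The only cause of interruption that Section 8 names is intercurrent illness.
- **Weights are imperfect.** Section 5.1.3 has CR participants tracking weight daily for two months and then at least every other week, while later in the same section daily weights are described. Early dropouts may have few weights and no 6-month visit. The TRE arm does not weigh at home.
- **This is a pilot.** It was not sized for hypothesis tests.

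All of these stand and limit the point. They do not remove it: nothing in the plan addresses adherence-related loss of the 9-month EI, although relevant data are already being collected.

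A reader might infer that the plan's statement about partial data is false, or that the model treats every dropout as a successful restrictor. The documents support neither: the statement is qualified, and the model conditions on arm, sex and baseline EI.

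**Conclusion.** The point holds as a gap in the handling of missing data for Benchmark 1. The benefit of partial data is limited here to baseline information, and adherence-related dropout is uncorrected. At a 2000 kcal/day baseline, the decision could change for completer reductions between 260 and about 287 to 291 kcal/day (remote), or between 274 and about 294 to 299 (in-person). The upper ends require zero restriction in everyone missing, which is an extreme assumption. With half restriction the bands end at about 272 and 284.

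It would be tempting to conclude that the expected loss by itself overturns Benchmark 1. It does not: outside these bands the decision is unaffected even with zero restriction in the missing, and a result near the 20% target passes comfortably. The calculations take the plan's SD of 250 kcal/day, its expected completer numbers and a zero intra-class correlation. The simulated false-pass rates rest on inputs that the documents do not give and are illustrative only.

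**What to change.** Keep the stated decision rule and add the following to Section 9.5.1:
1. Pre-specify auxiliary variables for missing 9-month EI: 6-month clinic weight change in all arms and, in the CR arms, the last available smart-scale weight change. Enter them as joint outcomes in the cLDA or as predictors in multiple imputation.
2. Report beside the Benchmark 1 result a delta or tipping-point analysis in which participants missing 9-month EI range from restricting like comparable completers down to no restriction. Agreement with the zero-restriction case should not be a condition of passing; that would add a worst-case hurdle that the plan does not intend.
3. State that baseline-only records address dropout related to baseline EI, not dropout related to adherence.

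This needs no new data and a modest amount of analysis work. The cost is a slightly more complex analysis, and it will help little for early dropouts with sparse weights, for whom the tipping-point report is the main safeguard.
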